# 7.3.12. Change in Lupus QoL Score

**Endpoint**: The Lupus Quality of Life (QoL) instrument will be assessed at Baseline, Weeks 24, 48 and 60, and any Flare or Endpoint visits that occur during the course of the trial. Data for the Lupus QoL will be captured on the *Lupus QoL* CRF page.

The Lupus QoL assessment is a 34 item questionnaire across 8 domains that is designed to find out how SLE affects a subject's life over the preceding 4 weeks. The physical health domain comprises item numbers 1–8, pain comprises 9–11, planning comprises 12–14, intimate relationships comprises 15 and 16, burden to others comprises 17–19, emotional health comprises 20–25, body image comprises 26–30, and fatigue comprises 31–34. Each of the 34 questions are answered on a 5-point scale, where 0 = all of the time, 1 = most of the time, 2 = a good bit of the time, 3 = occasionally, and 4 = never.

Item response scores are totaled for each domain and the mean raw domain score is obtained by dividing the total score by the number of items in that domain. The mean raw domain score is transformed to scores ranging from 0 (worst QOL) to 100 (best QOL) by dividing by 4 (the number of Likert responses [5 responses] minus 1) and then multiplying by 100, as below:

$$\frac{\text{mean raw domain score}}{4} \times 100 = \text{transformed score for domain}$$

Transformed domain scores are obtainable when at least 50% of the items are answered. The mean raw domain score is then calculated by totaling the item response scores of the answered items and dividing by the number of answered items. A nonapplicable response is treated as unanswered and the domain score is calculated as above.

Change from baseline in the Lupus QoL scores at Weeks 24, 48, and 60 will be computed for each subject.

**Analysis**: Analyses analogous to those specified in Section 7.3.6, *Changes in the SLICC/DI*, will be performed on the Lupus QoL scores.

Version: 1.0 Page 27 of 48

# 7.3.13. Recovery from Clinically Significant Disease Reactivation

The following endpoints will be assessed to describe the ability of subjects to recover from clinically significant disease reactivation.

# 7.3.13.1. Time from clinically significant disease reactivation to improvement in BILAG from maximum level during flare

**Endpoint:** See Section 7.2.1, *Computation of the Primary Endpoint*, for details on the definition of clinically significant SLE reactivation, and Section 7.3.4, *Probability of Experiencing a BILAG A Flare*, for more information on the BILAG and its scoring.

For each subject who experiences disease reactivation, time from clinically significant disease reactivation to improvement in BILAG from maximum level (at least an A or B) during the flare will be calculated in study days as: date of clinically significant disease reactivation – date of BILAG improvement. If multiple body systems have a BILAG flare at the visit, then the body system with the most severe score will be tracked for improvement; if multiple body systems have the same score (at least an A or B), then just one needs to show improvement.

Subjects who do not experience improvement in the BILAG prior to the end of their study participation or if the subject doesn't experience an increase in their BILAG score to a B or higher will be censored at their last visit date on study.

**Analysis**: Kaplan-Meier curves will be created for each treatment arm and will include 95% confidence intervals based on the Greenwood method.

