# 7.3.4. Probability of Experiencing a BILAG A Flare

Endpoint: The British Isles Lupus Assessment Group (BILAG) 2004 (2007 Revision) instrument will be completed at baseline and every follow-up visit, including any Flare or Endpoint visits, during the course of the 60 week study period for all subjects. Data for this assessment will be collected on the Modified BILAG: Constitutional, Modified BILAG: Musculoskeletal, Modified BILAG: Cardiorespiratory, Modified BILAG: Gastrointestinal, Modified BILAG: Ophthalmic, Modified BILAG: Renal, and Modified BILAG: Hematological CRF pages.

The rules for scoring the BILAG 2004 are in Appendix 14.4 *BILAG 2004 Index Scoring*. In each of the nine body system categories (constitutional, mucocutaneous, neuropsychiatric, musculoskeletal, cardiorespiratory, gastrointestinal, ophthalmic, renal, and hematological) subjects are assessed on a variety of disease activity criteria. Each category is then scored as an A, B, C, or D/E, where A indicates most severe disease activity and D/E indicates inactive/no disease activity. For this study the following additional scoring rules are applied:

 According to the scoring algorithm, D means "Inactive disease but previously affected", and E means "System never involved". Since we may not know whether the subject has ever experienced involvement in a particular system prior to starting the study, we will not attempt to distinguish between D and E. Subjects will be assigned the score "D/E" if they did not meet the criteria for A, B, or C at the particular visit.

Version: 1.0 Page 22 of 48

- 2. In the Renal category, some of the scoring rules require looking at previous measurements to assess change (e.g., 24 hour protein > 1g that has not decreased (improved) by >=25%). At Screening the BILAG is not collected as it is not required for eligibility purposes. As such, no previous BILAG assessment is available to refer to for applying such rules at the Day 0 visit and therefore subjects will not have a renal score assigned at Day 0.
- 3. In the Renal category, the original instrument includes an evaluation of proteinuria based on the protein:creatinine ratio derived from a 24-hour urine. For this study, the protein:creatinine ratio will typically be derived from the spot urine assessment although a 24-hour urine may be used if the spot urine assessment is not available.

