# 7.3.13.2. Time from clinically significant disease reactivation to recovery to baseline BILAG scores or BILAG C, whichever is worse

**Endpoint:** See Section 7.2.1, *Computation of the Primary Endpoint*, for details on the definition of clinically significant SLE reactivation, and Section 7.3.4, *Probability of Experiencing a BILAG A Flare*, for more information on the BILAG and its scoring.

For each subject who experiences disease reactivation, time from clinically significant disease reactivation to recovery to baseline BILAG scores or BILAG C, whichever is worse, will be calculated in study days as: date of clinically significant disease reactivation – date of BILAG recovery.

If a subject does not recover to their baseline BILAG score or BILAG C, whichever is worse, prior to the end of their study participation, or if the subject doesn't experience an increase in their BILAG score, then their BILAG score will be censored at their last visit date on study.

**Analysis**: Kaplan-Meier curves will be created for each treatment arm and will include 95% confidence intervals based on the Greenwood method.

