# 7.3.13.3. Cumulative excess systemic steroid dose from time of clinically significant disease reactivation to return to pre-flare dose or end of trial participation

**Endpoint:** See Section 7.2.1, *Computation of the Primary Endpoint*, for details on the definition of clinically significant SLE reactivation, and Section 7.3.8., *Systemic Steroid Dose*, for details on the definition of systemic steroids.

For each subject who experiences disease reactivation, excess systemic steroid dose will be summed from the time of clinically significant disease reactivation until the dose returns to pre-flare levels or the end of study participation, whichever occurs first. Excess systemic steroid dose will be defined as the total dose given for the flare – a subject's pre-flare steroid dose.

Version: 1.0 Page 28 of 48

Subjects who do not have an increase in their steroid use due to the flare will have their excess dose set to zero.

**Analysis**: Descriptive statistics (mean, standard deviation or standard error, median, minimum, maximum and number of subjects in a group) and 95% confidence intervals will be reported for the cumulative excess steroid dose in each treatment group.

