# 7.3.13.4. Time from clinically significant disease reactivation to return to pre-flare steroid dose.

**Endpoint:** See Section 7.2.1, *Computation of the Primary Endpoint*, for details on the definition of clinically significant SLE reactivation. Medications, including steroid use, are assessed at each study visit throughout the duration of the study and are collected on the *Prior/Concomitant Medications* CRF page.

For each subject who experiences disease reactivation, time from clinically significant disease reactivation to recovery to pre-flare steroid dose will be calculated in study days as: date of clinically significant disease reactivation – date of return to pre-flare steroid dose.

If a subject does not return to their pre-flare steroid dose prior to the end of their study participation, or if the subject does not have in increase in steroid dose due to their flare, then the variable will equal the duration of follow-up for that subject. Appropriate censor variables will be defined to indicate whether the time-to variable represents an event time or a censor time.

**Analysis**: Kaplan-Meier curves will be created for each treatment arm and will include 95% confidence intervals based on the Greenwood method.

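### SAP 7.3.13.1 keeps reactivated subjects who had no BILAG A or B in the improvement curve until their last visit; improvement is understated if any are still at risk when others improve

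*SAP*

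**What the plan says.** SAP 7.3.13 introduces four endpoints "to describe the ability of subjects to recover from clinically significant disease reactivation". Three are Kaplan-Meier curves by arm, each computed for every subject who reactivates. Each has its own rule for a subject whose score or dose did not rise.

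- **7.3.13.1, improvement in BILAG.** The event is improvement from a maximum of A or B during the flare. A subject who does not "experience an increase in their BILAG score to a B or higher will be censored at their last visit date on study".
- **7.3.13.2, recovery in BILAG.** The time from reactivation to "recovery to baseline BILAG scores or BILAG C, whichever is worse, will be calculated in study days". If the subject does not "experience an increase in their BILAG score, then their BILAG score will be censored at their last visit date on study". No minimum size of increase is set.
- **7.3.13.4, return to pre-flare steroid dose.** "if the subject does not have in increase in steroid dose due to their flare, then the variable will equal the duration of follow-up". On coding, the section says only: "Appropriate censor variables will be defined to indicate whether the time-to variable represents an event time or a censor time".

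The fourth endpoint, excess steroid dose in 7.3.13.3, treats the last group differently: "Subjects who do not have an increase in their steroid use due to the flare will have their excess dose set to zero".

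Protocol 2.2.1 and 8.3.2.2 define the population for these endpoints as all subjects who reactivate. Neither says how to handle a subject with no rise.

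**The concern.** Kaplan-Meier treats a censored subject as someone who could still have the event later. A subject with no A or B during the flare cannot improve from A or B. Under 7.3.13.1 that subject stays in the risk set until last visit and dilutes every improvement that occurs meanwhile. A section meant to describe ability to recover then shows people with nothing to recover from as people who have not recovered.

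The rule has a second effect. It turns on an increase to B or higher, not on having a B. Read literally, it also censors a subject who was at B at baseline, stayed at B through the flare and later improved. SAP 7.3.13.2 allows for such baselines, because its target is the worse of baseline and C.

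Recovery after reactivation is a stated secondary objective (Protocol 2.2.1). If the share of such subjects differed between arms, the descriptive comparison would be distorted too; the documents do not establish that it would.

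**Working it through.** The plan gives no figure for these endpoints, so there is nothing to reproduce. All recovery times, shares and follow-up patterns below are assumptions.

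**1. Can such subjects exist?** Yes. SAP 7.3.13.1 and 7.3.13.2 each carry a rule for them. Under SAP 7.2.1 one flare criterion is enough, and a new major immunosuppressive is one of the severe criteria. Sensitivity analysis 3 in SAP 7.2.3 is written for subjects whose only qualifying change is that treatment. Criterion 2c still refers to clinical activity, so this shows a possible route, not a count.

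**2. 7.3.13.1, general size.** Let f be the share of reactivated subjects with no A or B during the flare, and F(t) the improvement probability in the others. If both groups are censored alike, the curve estimates (1 − f)·F(t). Take F(t) = 1 − 2^(−t/8), an 8-week median, so F(24) = 1 − 2^(−3) = 0.875.

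| f | (1 − f) × 0.875 at week 24 | Apparent median (weeks) |
|---|---|---|
| 0 | 0.875 | 8 |
| 0.1 | 0.79 | 9.4 |
| 0.2 | 0.70 | 11.3 |
| 1/3 | 0.58 | 16 |

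With f = 0.2, a 4-week median gives 0.79 instead of 0.98, and a 16-week median gives 0.52 instead of 0.65. The bias shrinks if these subjects leave early: in simulation with f = 0.2, an 8-week median and the others followed for 8 to 56 weeks, the week-24 value is 0.849 if they are censored at week 8 and 0.864 if at week 4. It is nil if all leave before the first improvement. The formula does not cover the subject who stays at B from baseline, who can improve.

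**3. 7.3.13.1, worked example.** Four subjects with an A or B improve at weeks 4, 8, 12 and 16. Add k subjects with neither, censored at week 40. For k = 2, week 8 is 1 − (5/6)(4/5) = 0.33.

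| k | Week 8 | Week 16 | Median (weeks) |
|---|---|---|---|
| 0 | 50% | 100% | 8 |
| 1 | 40% | 80% | 12 |
| 2 | 33% | 67% | 12 |
| 3 | 29% | 57% | 16 |

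In 20,000 random data sets, adding such subjects never raised the curve and lowered it somewhere in 18,009.

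**4. 7.3.13.2.** A rise from D/E to C already meets the target, so it may count as recovery at time 0. Use the same four subjects, now as those who rose above the target (50% at week 8). Two no-increase subjects give 33%, two D/E-to-C subjects give 67%, and one of each gives 50%. The time point matters too. With one of each, the curve is 33% against 25% at week 4 and 83% against 100% at week 16.

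**5. 7.3.13.4.** Three of four subjects return to dose at weeks 4, 8 and 12, and the fourth is censored at week 30. Add two no-increase subjects with 40 weeks of follow-up. Week 12 falls from 75% to 1 − (5/6)(4/5)(3/4) = 50% under either coding. At week 40 the curve is 50% if they are censored and 100% if they are coded as events.

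**6. Scale.** SAP section 12 reports 8 of the first 80 subjects reactivated. At that rate 120 × 8/80 = 12 would reactivate, or 6 per arm if evenly split. In an arm of 6, with an 8-week median and follow-up of 8 to 56 weeks, making one of them a no-rise subject moves the mean week-24 estimate from 0.864 to 0.726. That is about one standard deviation of the estimate (0.12 to 0.22 over the arm sizes of 3 to 9 that were tried).

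**The case against.** The strongest reply is that this is a choice of estimand. The protocol's population is all reactivated subjects, and the 7.3.13.1 curve is a valid probability of an observed improvement in that population, apart from any subject who stays at B from baseline and later improves. That stands: understated is true only relative to subjects who had something to improve from. But that group is the one the section's stated purpose concerns, and the censoring rule for no-rise subjects comes from the SAP, not the protocol.

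Second, restricting the curve conditions on a rise that may come after reactivation, so a subject who peaks later cannot improve before the peak. That also stands and is a cost of the fix. Reactivation is itself post-randomisation, so these curves were never a randomised comparison.

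Third, Protocol 8.3.2.2 already warns of bias in the recovery endpoints. Its warning concerns subjects who reactivate near the end of follow-up, not subjects who can never have the event.

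Fourth, everything is exploratory, the sizes are assumed, and about 12 reactivations would give imprecise curves in any case. All true; this limits the weight of the point.

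**Conclusion.** The defect is explicit in 7.3.13.1. Subjects with no A or B lower the curve whenever one is still at risk as another improves, and the literal rule also discards improvement in a subject who stays at B from baseline. The size depends on their number and follow-up, which the documents do not give. A share of 10% to one third with an 8-week median would take week-24 improvement from 0.875 to between 0.79 and 0.58.

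A reader might infer more than this.

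- That all three curves are biased downward. In 7.3.13.4 the coding is left open; censoring is only the natural reading, and event coding would raise the tail. In 7.3.13.2 no-increase subjects lower the curve while D/E-to-C subjects may raise it, so the net direction is undetermined. Recovery at time 0 is itself inferred from the target, not stated.
- That everyone censored under the 7.3.13.1 rule is incapable of the event. The subject who stays at B from baseline is the exception.
- That the comparison between arms is biased. This would need the share to differ by arm, which is possible but not established.

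The zero excess dose in 7.3.13.3 is sensible in itself. It shows only that the SAP can recognise subjects with nothing to recover from. The primary analysis is unaffected.

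**What to change.** - **7.3.13.1:** limit the curve to reactivated subjects with a BILAG A or B during the flare, whatever the baseline score.
- **7.3.13.2:** limit it to those whose BILAG is worse than the recovery target.
- **7.3.13.4:** limit it to those whose steroid dose was raised for the flare. The coding of subjects with no increase then no longer arises.
- For each curve, report by arm the number and percent of reactivated subjects left out, so that the protocol's full reactivated population stays visible.
- Record the change in SAP section 12.

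The cost is wording in three subsections, the by-arm counts and one section 12 entry; no new data are needed. The price is fewer subjects per curve, and curves conditional on a rise that may follow reactivation. They should be labelled descriptive only.

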# 7.3.13.2. Time from clinically significant disease reactivation to recovery to baseline BILAG scores or BILAG C, whichever is worse

**Endpoint:** See Section 7.2.1, *Computation of the Primary Endpoint*, for details on the definition of clinically significant SLE reactivation, and Section 7.3.4, *Probability of Experiencing a BILAG A Flare*, for more information on the BILAG and its scoring.

For each subject who experiences disease reactivation, time from clinically significant disease reactivation to recovery to baseline BILAG scores or BILAG C, whichever is worse, will be calculated in study days as: date of clinically significant disease reactivation – date of BILAG recovery.

If a subject does not recover to their baseline BILAG score or BILAG C, whichever is worse, prior to the end of their study participation, or if the subject doesn't experience an increase in their BILAG score, then their BILAG score will be censored at their last visit date on study.

**Analysis**: Kaplan-Meier curves will be created for each treatment arm and will include 95% confidence intervals based on the Greenwood method.

# 7.3.13.3. Cumulative excess systemic steroid dose from time of clinically significant disease reactivation to return to pre-flare dose or end of trial participation

**Endpoint:** See Section 7.2.1, *Computation of the Primary Endpoint*, for details on the definition of clinically significant SLE reactivation, and Section 7.3.8., *Systemic Steroid Dose*, for details on the definition of systemic steroids.

For each subject who experiences disease reactivation, excess systemic steroid dose will be summed from the time of clinically significant disease reactivation until the dose returns to pre-flare levels or the end of study participation, whichever occurs first. Excess systemic steroid dose will be defined as the total dose given for the flare – a subject's pre-flare steroid dose.

Version: 1.0 Page 28 of 48

Subjects who do not have an increase in their steroid use due to the flare will have their excess dose set to zero.

**Analysis**: Descriptive statistics (mean, standard deviation or standard error, median, minimum, maximum and number of subjects in a group) and 95% confidence intervals will be reported for the cumulative excess steroid dose in each treatment group.

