## 2.2 Secondary Objectives

### 2.2.1 Secondary Disease Activity Objectives

- To describe the effect of MMF withdrawal on measures of disease activity (including time to flare and severity of flare) in aggregate and in subgroups defined by demographics, disease manifestation (renal disease/extra-renal disease) and by baseline MMF dosing group (< 2000 mg per day / ≥ 2000 mg per day).
- To describe the effect of MMF withdrawal on damage accrual, needed medications, and subject quality of life.
- To describe the effect of MMF withdrawal on time to recovery from clinically significant disease reactivation and needed medications in the subgroup defined by disease reactivation during follow-up.

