# **Secondary Disease Activity Endpoints**

- Time from Day 0 to clinically significant disease reactivation (as defined in Section 3.2, Description of Primary Endpoint). The time of clinically significant disease reactivation is defined as the date of the first SELENA-SLEDAI\* assessment that meets (or goes on to meet) the criteria in Section 3.2, Description of Primary Endpoint.
- The probability of experiencing any SELENA-SLEDAI\* flare and the probability of experiencing any severe SELENA-SLEDAI\* flare by Week 60, in aggregate and within subgroups defined by disease manifestation (renal disease / extra-renal disease) and by baseline MMF dosing group (<2000 mg per day / ≥ 2000 mg per day).
- Time from initiation of withdrawal to first SELENA-SLEDAI\* flare and time to first severe SELENA-SLEDAI\* flare.
- The probability of experiencing any BILAG\* A flare by Week 60.
- Proportion of subjects in the renal subgroup with BILAG\* Renal A flare by Week 60
- Change in SLICC/DI from baseline to Weeks 24, 48, and 60.
- The probability of adding aggressive adjunctive therapy to MMF (including IV immunoglobulin or rituximab) or change in MMF therapy to cytotoxic drug (e.g., cyclophosphamide) due to flare.
- Cumulative systemic steroid dose (PO, IV, IM) at Week 60.
- Change in FACIT fatigue score from baseline to Weeks 24, 48, and 60.
- Change in SF-36® PF and PCS domains from baseline to Weeks 24, 48, and 60.
- Change in Lupus QoL-US© from baseline to Weeks 24, 48, and 60.
- The following endpoints will be assessed to describe the ability of subjects to recover from clinically significant disease reactivation:
  - Time from clinically significant disease reactivation to improvement in BILAG\* from maximum level during flare;
  - Time from clinically significant disease reactivation to recovery to baseline BILAG\* scores or BILAG\* C, whichever is worse;
  - Cumulative excess systemic steroid dose from time of clinically significant disease reactivation to return to pre-flare dose or end of trial participation;
  - Time from clinically significant disease reactivation to return to pre-flare steroid dose.

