# 7.2. Primary Endpoint

# 7.2.1. Computation of the Primary Endpoint

The primary endpoint is the probability in each arm of experiencing clinically significant disease reactivation by 60 weeks after randomization. The 60-week time point is to allow 48 weeks of observation off MMF in the withdrawal arm and minimize dropout, which is likely to occur as the trial lengthens. Clinically significant SLE reactivation requires both:

- 1) A SELENA-SLEDAI\*-defined mild/moderate or severe flare, and
- 2) Increased immunosuppressive therapy on a sustained basis as defined by one of the following criteria:
  - a. Sustained activity: Subject has significant prolonged SLE flare requiring steroid increase/burst to ≥ 15 mg/day prednisone (or its equivalent) for more than four weeks.
  - b. Frequent relapsing/remitting:
    - Subject flares requiring an increase/burst of steroids and is successfully tapered to < 15 mg/day within four weeks, but this occurs on two or more occasions. or
    - ii. Intra-articular, intra-muscular or IV steroids, on more than one occasion.
  - c. Clinical activity of sufficient severity to warrant resumption of or an increased dose of MMF or addition of other major immunosuppressive including azathioprine or methotrexate. Regardless of steroid use, if the investigator observes disease activity of sufficient severity to warrant resumption, addition or increase in dosage of major immunosuppressant in the setting of a SELENA-SLEDAI\*-defined flare, subject has met the primary endpoint.

Version: 1.0 Page 16 of 48

\*ALE06 will typically use a spot urine protein:creatinine ratio rather than a 24-hour urine assessment for the SELENA-SLEDAI. However, if indicated, results from a 24-hour urine collection may be used.

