# **Endpoint:**

For each subject, a yes/no variable will be assigned to indicate whether a subject has met the primary endpoint of clinically significant disease reactivation between Day 0 and Week 60, as defined above.

Subjects who terminate early from the study, and who had not previously met primary endpoint, will be handled as follows:

- 1. Subjects who do not have a mild/moderate or severe SELENA-SLEDAI flare at their last study visit will be categorized as not experiencing clinically significant disease reactivation.
- 2. Subjects who have a mild/moderate or severe SELENA-SLEDAI flare at their last study visit:
  - a. Subjects will be categorized as experiencing clinically significant disease reactivation for the following three scenarios:
    - i. Subject has a SELENA-SLEDAI mild/moderate or severe flare at the time of early termination, and a steroid increase/burst to ≥ 15 mg/day prednisone that is sustained through end of study.
    - Subject previously experienced a flare requiring either intraarticular, intra-muscular or IV steroids, or an increase/burst of steroids that was successfully tapered to < 15 mg/day within four

Version: 1.0 Page 18 of 48

<sup>1 For ALE06, prednisone > 0.5 mg/kg/day is categorized as a severe SELENA-SLEDAI flare if the duration is >2 weeks. Increases in prednisone >0.5 mg/kg/day but for ≤2 weeks will be categorized as mild/moderate SELENA-SLEDAI flares.

weeks, and is experiencing a severe flare at the time of early termination.

- iii. Subject has a SELENA-SLEDAI severe flare based on the following clinical components: SLEDAI score; New/Worse disease, and Increase in PhGA without considering prednisone or other treatments
- b. Subjects experiencing flare at the time of early termination, but who do not met the criteria in 2.a. above, will be classified as not experiencing clinically significant disease reactivation.

These cases will be re-categorized under sensitivity analyses for the primary endpoint (see 7.2.3).

The time of clinically significant disease reactivation is defined as the date of the first SELENA-SLEDAI assessment that meets (or goes on to meet) the criteria for clinically significant SLE reactivation. The time-to-event will be defined as the interval: date of disease reactivation – date of Day 0 visit. Subjects who do not experience clinically significant disease will be censored at the last visit date on study.

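### For relapsing (criterion 2b) subjects who settle between flares, the recovery endpoints in SAP 7.3.13 end before reactivation has been met, and the excess steroid dose omits the burst that completed the criterion

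*SAP*

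**What the plan says.** SAP 7.2.1 (Endpoint) sets the reactivation date as the "date of the first SELENA-SLEDAI assessment that meets (or goes on to meet) the criteria for clinically significant SLE reactivation". Protocol 3.3.1 uses the same rule.

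Criterion 2b in SAP 7.2.1 has two branches, and each needs at least two occasions:

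- 2b.i: a steroid burst "successfully tapered to < 15 mg/day within four weeks, but this occurs on two or more occasions".
- 2b.ii: "Intra-articular, intra-muscular or IV steroids, on more than one occasion".

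The four recovery endpoints run from the reactivation date:

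- 7.3.13.1 ends at BILAG improvement from the worst level (A or B) reached in the flare.
- 7.3.13.2 ends at recovery to baseline BILAG or C, whichever is worse.
- 7.3.13.3 is excess systemic steroid dose "summed from the time of clinically significant disease reactivation until the dose returns to pre-flare levels or the end of study participation", whichever comes first. It speaks of one flare only.
- 7.3.13.4: "time from clinically significant disease reactivation to recovery to pre-flare steroid dose will be calculated in study days".

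None of the four has a rule for a second qualifying flare, a condition that recovery be sustained, or a separate start for 2b. Together they serve the objective in Protocol 2.2.1 on "time to recovery from clinically significant disease reactivation and needed medications in the subgroup defined by disease reactivation during follow-up".

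**The concern.** The start date looks back to the first flare, while the stop is the first return after it. For a 2b subject these two rules can enclose only the first flare. The subject is then recorded as recovered from a reactivation whose criteria have not yet been met, and the flare that met them falls outside the recovery window.

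At stake is a stated secondary objective. The affected subjects are those the plan classes as relapsing, and for them the error runs towards quick recovery and low excess steroid exposure. If the arms differ in how many subjects qualify through 2b, the per-arm recovery summaries differ partly for that reason.

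**Working it through.** The documents give no figure for the recovery endpoints, so there is none to reproduce. The check applies the SAP's rules to worked dose histories.

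**Inputs from the documents**

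- Start date, and two occasions needed for 2b: SAP 7.2.1.
- Stop rules: SAP 7.3.13.1 to 7.3.13.4.
- 2b.i taper threshold: below 15 mg/day (SAP 7.2.1). Stable baseline dose: at most 10 mg/day (Protocol 5.5.2).
- Systemic steroids are oral, IV and IM only (SAP 7.3.9).
- 8 of the first 80 subjects had reactivated (SAP 12, item 4).

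**Assumed, for illustration only:** each burst is 20 mg for 14 days, then 14 mg for 7 days; 84 days lie between bursts; the pre-flare dose p is 0, 5 or 10 mg/day.

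**Step 1. Order of dates.** Let t1 be the first flare, tR the first return to pre-flare dose, and t2 the flare that completes 2b. The start is t1 and the stop is tR. If tR falls before t2, the whole endpoint lies before the criteria are met.

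**Step 2. Dose returns to p between bursts.** Excess per burst = 14 × (20 − p) + 7 × (14 − p).

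| p (mg/day) | Counted by 7.3.13.3 | Both bursts | Captured |
|---|---|---|---|
| 0 | 280 + 98 = 378 mg | 756 mg | 50% |
| 5 | 210 + 63 = 273 mg | 546 mg | 50% |
| 10 | 140 + 28 = 168 mg | 336 mg | 50% |

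Time to return under 7.3.13.4 is 21 days. The final return comes 21 + 84 + 21 = 126 days after the first flare.

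Two variants:

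- Larger second burst (40 mg for 14 days, then 14 mg for 7 days, p = 5): the second burst is 14 × 35 + 7 × 9 = 553 mg. Captured: 273 / (273 + 553) = 273 / 826 = 33%.
- Two single IM doses of 80 mg equivalent: 80 of 160 mg is captured (50%), and recovery is recorded at 1 day.

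**Step 3. Dose held at 12.5 mg/day between bursts.** This satisfies 2b.i but stays above p. The interval adds 84 × (12.5 − p) = 1050, 630 or 210 mg. Totals are 1806, 1176 and 546 mg. All of it is counted, and time to return is 126 days. The problem does not arise.

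**Step 4. BILAG endpoints.** The clock stops early only if an improvement (7.3.13.1) or recovery (7.3.13.2) is observed between flares. A subject who never reaches B or worse is censored under 7.3.13.1, and one with no BILAG increase is censored under 7.3.13.2.

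**Step 5. How many subjects.** 8 / 80 = 10%. If that rate held for 120 subjects, there would be about 12 reactivations. The documents do not give the 2b share. An assumed 10% to 40% gives 1.2 to 4.8, or about 1 to 5 subjects over both arms.

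**The case against.** A reader might infer that every relapsing subject is scored as recovered after the first burst. The documents do not support that. The 2b.i threshold (below 15 mg/day) is not the stop rule (pre-flare dose, normally at most 10 mg/day), and Step 3 shows a qualifying subject counted in full. Nor are 2b subjects as a class the fastest recoverers. Intra-articular injections lie outside the systemic definition, so a subject with only those shows no systemic increase and would be censored under 7.3.13.4. The BILAG endpoints need an observed improvement.

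A reader might also infer that the second burst disappears from the trial's results. It does not: the 60-week total and excess doses in SAP 7.3.9 still count every systemic burst.

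Further points on the other side are fair. Secondary analyses are exploratory and descriptive, and 7.3.13 plans per-arm curves and summaries without a between-arm test. Protocol 8.3.2.2 already warns of bias in these endpoints from informative censoring. The SAP does not say outright how its dating rule applies to 2b. Time to first return is also a legitimate quantity in its own right.

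These points narrow the scope and lower the stakes. They leave the core standing: for 2b subjects who do return between flares, the stated rules end the recovery endpoint before reactivation is met. The 7.3.9 totals do not measure recovery from reactivation, and the protocol's censoring warning concerns a different mechanism.

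**Conclusion.** The concern holds for a defined subset: 2b subjects whose systemic steroid dose or BILAG reaches the recovery level between the first flare and the one that completes the criterion. For them, 7.3.13.1, 7.3.13.2 and 7.3.13.4 can record recovery too early, and 7.3.13.3 drops the completing burst. The loss is 50% of excess dose with two equal bursts and 33% captured (67% lost) in the larger-second-burst example. These percentages rest on assumed dose histories.

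The effect on the arm-level results cannot be computed, because neither the number of 2b subjects nor their doses are given. It might be tempting to say that early recovery is overstated by the 2b share, for example 10 to 40 percentage points. That only restates an assumed share and requires every such subject to recover between flares. With few reactivations, however, one or two affected subjects could visibly move a curve or a mean.

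The conclusion also rests on reading the dating rule as pointing to the first flare, which is natural but not spelled out for 2b. The primary endpoint, SAP 7.3.1 and the sample size are not affected.

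**What to change.** In SAP 7.3.13, for subjects who qualify through 2b:

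- **7.3.13.3:** sum excess systemic dose from the first flare until the dose returns to its pre-flare level after the completing burst or injection, or until participation ends. State that the pre-flare dose is the one before the first of the qualifying flares.
- **7.3.13.1, 7.3.13.2 and 7.3.13.4:** do not count improvement, recovery or return before the criteria are complete. Start the clock at the flare assessment that completes 2b.
- Keep the first-flare date for the primary endpoint and 7.3.1, and state there how the dating rule applies to 2b.
- List the change in SAP Section 12, since it departs from the reactivation date in Protocol 3.3.1.

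The cost is a few sentences. The flare/endpoint and medication CRF pages already named in the SAP should supply the dates and doses. The downsides are later recovery dates, longer recorded recovery times where the second flare is slower to settle, and less remaining follow-up for 2b subjects, hence more censoring. The restart also removes the interval between flares from the clock. In the Step 3 example, time to return falls from 126 to 21 days, so the interval from first flare to completion of 2b should be reported alongside.
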